**Note: Cycle 1 Day15: The morning dose of alisertib should be taken prior to Cycle 1 Day15 blood draws.**

## 6.2 Arm 2 (Alisertib with Fulvestrant)

One treatment cycle = 28 ( $\pm 3$ ) days

- 6.2.1 Patients randomized to Arm 2 will receive the combination of fulvestrant and alisertib until progression (PD) or intolerability and then enter the event monitoring phase of the protocol.
- 6.2.2 Patients will receive a loading dose of fulvestrant unless fulvestrant was the most recent therapy prior to registration and most recent dose was  $\leq 30$  days and  $>21$  days prior to C1D1.
- 6.2.3 On the days both fulvestrant and alisertib are given, alisertib should be taken before fulvestrant is administered.

Agent	Dose	Schedule	Route	Retreatment
Fulvestrant	500 mg	Day 1 and Day 15 of Cycle 1 Day 1 of Cycle 2 and all cycles thereafter	intramuscular injection	every 28 ( $\pm$ 3) days until disease progression
Alisertib	50 mg BID*	Days 1-3, 8-10, 15-17	orally	every 28 ( $\pm$ 3) days until disease progression

\* Doses should be taken 12 hours apart with a minimum of 6 hours in between

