## 1. STUDY DESIGN/SUMMARY

Patients with ER+ metastatic breast cancer are typically treated with multiple lines of endocrine therapy, and tumor response rates to serial agents after first-line therapy tend to decrease. This coincides with ER $\alpha$  down-regulation, aggressive tumor behavior, and poor clinical outcomes. Novel therapies to overcome endocrine resistance are needed. Currently, there are no drugs either FDA-approved or in development to reverse endocrine resistance that results from down-regulation of the ER $\alpha$ .

Our preclinical data suggests that in ER+ breast cancer, Aurora A Kinase (AAK) is associated with the development of epithelial to mesenchymal transition (EMT) reprogramming and the expansion of breast tumor initiating cells that are ER $\alpha$ low/- and resistant to endocrine therapy. We postulate that this is a mechanism by which ER down-regulation occurs. Thus targeted treatment with alisertib, an AAK inhibitor, is projected to reverse EMT and restore tumor ER $\alpha$  expression and sensitivity to endocrine therapy.

A randomized phase II trial to evaluate alisertib alone and in combination with fulvestrant is proposed. Based on our preclinical data, we project that the patients most likely to derive benefit from treatment with alisertib will be those that are resistant to endocrine therapy, so this will be our target population. Given the striking clinical activity of single agent alisertib observed in the cohort of heavily pretreated, ER+ metastatic breast cancer patients (n=26, CBR 88% and PFS 7.9 months), additional exploration of single agent activity in this patient population is warranted and justified. Based on our preclinical data, we project that the combination of alisertib and fulvestrant will result in superior clinical outcomes compared to alisertib alone. For this reason a head-to-head comparison of these two treatment strategies was selected.

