### 2.3 Correlative Research

- 2.3.1 To assess the changes in Aurora A kinase, SMAD5 and SOX2 expression and phosphorylation in tumor tissue after first cycle of assigned treatment
- 2.3.2 To assess the changes in ER expression and function in tumor tissue after the first cycle of assigned treatment

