4.1.5 Prior treatment

- No more than two prior chemotherapy regimens in the metastatic setting.
- Prior treatment with fulvestrant in the metastatic setting is required, except for patients with a history of ER-negative metastatic breast cancer
- Unlimited prior endocrine therapy regimens in the metastatic setting are allowed

- No prior treatment with an Aurora Kinase inhibitor (either an Aurora A or pan-Aurora kinase inhibitor)
- 4.1.6 Disease that is measurable where:
- A non-nodal lesion is considered measurable if its longest diameter can be accurately measured as  $\geq 2.0$  cm with chest x-ray, or as  $\geq 1.0$  cm with CT scan, CT component of a PET/CT, or MRI.
  - A malignant lymph node is considered measurable if its short axis is  $\geq 1.5$  cm when assessed by CT scan (CT scan slice thickness recommended to be no greater than 5 mm).
- Note:** Tumor lesions in a previously irradiated area are not considered measurable disease.
- Note:** Disease that is measurable by physical examination only is not eligible.
- 4.1.7 No history of tumors involving spinal cord or heart.
- 4.1.8 Fully recovered from acute, reversible effects of prior therapy regardless of interval since last treatment
- EXCEPTION:** Neuropathies – if Grade 2 neuropathies have been stable for at least 3 months since completion of prior treatment, patient is eligible.
- 4.1.9a ECOG Performance Status: 0 or 1 (See [Appendix I](#))
- 4.1.9b No requirement for constant administration of proton pump inhibitor, H2 antagonist, or pancreatic enzymes (see [Appendix IV](#))
- 4.1.9c Willing to limit daily alcohol intake to the following: one 12-oz glass of beer, one 6-oz glass of wine, or one 1.5-oz portion of 80-proof alcohol.
- 4.1.9d No uncontrolled intercurrent illness including, but not limited to:
- ongoing or active infection
  - symptomatic congestive heart failure
  - unstable angina pectoris
  - uncontrolled symptomatic cardiac arrhythmia
  - uncontrolled hypertension (defined as blood pressure  $>160/90$ )
- 4.1.9e No history of uncontrolled sleep apnea syndrome and other conditions that could result in excessive daytime sleepiness, such as severe chronic obstructive pulmonary disease, or requirement for supplemental oxygen.
- 4.1.9f No other active second malignancy other than non-melanoma skin cancers and in situ cervical cancers within 5 years of registration.

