## 4.2 Registration Eligibility Criteria

- 4.2.1  $\leq 28$  days post pre-registration
- 4.2.2 Central Laboratory ER determination completed.
- 4.2.3 The following laboratory values obtained  $\leq 14$  days prior to randomization:
- Absolute neutrophil count (ANC)  $\geq 1500/\text{mm}^3$
  - Platelet count  $\geq 100,000/\text{mm}^3$
  - Hemoglobin  $\geq 9.0$  g/dL
  - Total bilirubin  $\leq \text{ULN}$
- NOTE: If total bilirubin is out of range then direct bilirubin must be  $\leq \text{ULN}$

- Alanine transaminase (ALT)  $\leq 2.5 \times \text{ULN}$  ( $\leq 5 \times \text{ULN}$  for patients with liver involvement)
- Calculated creatinine clearance must be  $\geq 45$  ml/min using the Cockcroft-Gault formula below:

Cockcroft-Gault Equation:	
Creatinine clearance for females =	$\frac{(140 - \text{age})(\text{weight in kg})(0.85)}{(72)(\text{serum creatinine in mg/dL})}$

- 4.2.4 ECOG Performance Status: 0 or 1 (See [Appendix I](#))
- 4.2.5 Life expectancy of  $\geq 6$  months.
- 4.2.6 Willing to provide blood and tissue for correlative research purposes.

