### 4.3 Registration Exclusion Criteria

- 4.3.1 Any of the following therapies prior to registration:
- Chemotherapy  $\leq 21$  days
  - Immunotherapy  $\leq 21$  days
  - Biologic therapy (includes monoclonal antibodies)  $\leq 21$  days
  - Hormonal therapy  $\leq 14$  days except fulvestrant  $\leq 21$  days
  - Targeted therapies including CDK 4/6 inhibitors (e.g. palbociclib, abemaciclib, ribociclib, etc.) and mTOR inhibitors (e.g. everolimus)  $\leq 21$  days
  - Other investigational agents  $\leq 21$  days
  - Radiation therapy  $\leq 14$  days
  - Minor surgical or interventional procedure  $\leq 7$  days
  - Major surgical procedure  $\leq 21$  days
- 4.3.2 Administration of myeloid growth factors or platelet transfusion  $\leq 14$  days prior to registration.
- 4.3.3 Systemic infection requiring IV antibiotic therapy  $\leq 14$  days prior to registration.
- 4.3.4 Treatment with clinically significant enzyme inducers, such as the enzyme-inducing antiepileptic drugs phenytoin, carbamazepine or phenobarbital, or rifampin, rifabutin, rifapentine or St. John's wort  $\leq 14$  days prior to registration.
- 4.3.5 Require constant administration of proton pump inhibitor, H2 antagonist, or pancreatic enzymes (see Appendix IV).
- 4.3.6 Development of visceral crisis since pre-registration.  
NOTE: Visceral crisis is moderate-to-severe organ dysfunction as assessed by symptoms and signs, laboratory studies, and rapid progression of disease.
- 4.3.7 History of brain metastases.

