### 5.2.3 All Institutions

5.2.3.1 Documentation of IRB approval must be on file in the [REDACTED] before an investigator may register any patients.

In addition to submitting initial IRB approval documents, ongoing IRB approval documentation must be on file (no less than annually) at the [REDACTED]. If the necessary documentation is not submitted in advance of attempting patient registration, the registration will not be accepted and the patient may not be enrolled in the protocol until the situation is resolved.

When the study has been permanently closed to patient enrollment, submission of annual IRB approvals to the Registration Office is no longer necessary.

5.2.3.2 Prior to accepting the registration, registration/randomization application will verify the following:

- IRB approval at the registering institution
- Patient eligibility
- Existence of a signed consent form
- Existence of a signed authorization for use and disclosure of protected health information

5.2.3.3 At the time of registration, the following will be recorded:

- Patient has/has not given permission to store and use his/her sample(s) for future research of cancer.
- Patient has/has not given permission to store and use his/her sample(s) for future research to learn, prevent, or treat other health problems.
- Patient has/has not given permission for someone to contact them about future participation in more research
- Patient has/has/not given permission to have coded genetic information and coded medical information placed in password protected, secured database for research analyses.

5.2.3.4 Treatment on this protocol must commence at a TBCRC institution under the supervision of a medical oncologist.

5.2.3.5 Treatment cannot begin prior to randomization and must begin  $\leq 7$  days after randomization.

5.2.3.6 Pretreatment tests/procedures (see Section 11) must be completed within the guidelines specified on the test schedule. Prior to registration/randomization a research biopsy of metastatic breast tissue must be taken for central pathologic review.

5.2.3.7 All required baseline symptoms must be documented and graded.

5.2.3.8 Study drug is available on site.

5.2.3.9 Blood draw kit is available on site.

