### 8.2.1 Background

Fulvestrant is an estrogen receptor antagonist. Fulvestrant competitively binds to estrogen receptors on tumors and other tissue targets, producing a nuclear complex that causes a dose-related down-regulation of estrogen receptors and inhibits tumor growth.

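### Change in tumor ER after Cycle 1 is read without time since last fulvestrant, so in recently treated Arm 1 patients wash-out cannot be told apart from ER restoration by alisertib

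*Combined protocol and SAP*

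**What the plan says.** The protocol's hypothesis (section 1) is that alisertib "is projected to reverse EMT and restore tumor ER" alpha expression and, with it, endocrine sensitivity. Objective 2.3.2 follows from this: "To assess the changes in ER expression and function in tumor tissue after the first cycle of assigned treatment".

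On exposure to fulvestrant, section 4.1.5 states: "Prior treatment with fulvestrant in the metastatic setting is required, except for patients with a history of ER-negative metastatic breast cancer". Section 8.2.1 says that the drug "causes a dose-related down-regulation of estrogen receptors and inhibits tumor growth", and section 8.2.5 gives an elimination half-life of about 40 days for the 250 mg dose. Section 4.3.1 excludes fulvestrant in the 21 days before registration. No interval is set between the last injection and the baseline biopsy, which is taken in the pre-registration period of up to 28 days (4.2.1, 11.1).

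Arm 1 receives no fulvestrant in Cycle 1 (6.1). In Arm 2, section 6.2.2 takes account of recent use: "Patients will receive a loading dose of fulvestrant unless fulvestrant was the most recent therapy prior to registration" and the last dose fell 22 to 30 days before Cycle 1 Day 1.

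Section 17.4.4 correlates, within each arm, the percent change in tissue ER alpha with maximum tumor shrinkage (Spearman). No part of 17.4 says how the ER change itself will be summarised or read. Neither 17.3 nor 17.4 uses time since last fulvestrant.

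**The concern.** Arm 1 is the natural place to look for ER restoration by alisertib, because Arm 2 also receives a drug that lowers ER. But an Arm 1 patient who came to the trial soon after fulvestrant is losing that drug between the two biopsies. If ER recovers as fulvestrant clears, it rises in the direction that the hypothesis predicts, even if alisertib does nothing to ER.

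Randomisation does not remove this. Arm 1 washes out while Arm 2 is dosed again, so the arms would diverge on ER with no alisertib effect at all, and the planned analysis is within arm in any case. What is at stake is the reading of Objective 2.3.2. The response comparison is not involved.

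**Working it through.** **Plan's own figure.** Section 17.4.4 states no sample size or power. The nearest figure is in 17.4.3: 90% power for a baseline Spearman correlation of 0.35, n = 81, two-sided 0.05. By Fisher's z, Φ(atanh(0.35) × √78 − 1.96) = 0.898, which agrees. Nothing here disputes it.

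**Inputs.** Half-life H = 40 days (8.2.5, stated for 250 mg), varied from 30 to 50 as an assumption. Baseline biopsy to registration is 0 to 28 days (4.2.1). Section 5.2.3 says "Treatment cannot begin prior to randomization and must begin" within 7 days. The cycle is 28 ± 3 days (6.1), and the second biopsy is 0 to 4 days before Cycle 2 (9.2.1). First-order loss is assumed, with no fulvestrant between the baseline biopsy and Cycle 1 Day 1.

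**Interval between biopsies.** Short case: biopsy, registration and start on one day, 28-day cycle, second biopsy 4 days early: 28 − 4 = 24 days. Long case: 28 + 7 + 31 = 66 days. These are working values rather than strict limits. The central ER result must be available before registration (4.2.2), which makes the short case unlikely. A 25-day cycle would allow 21 days, and treatment holds could exceed 66.

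**Fall in residual drug, 1 − 2^(−t/H).**

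| Half-life | 24 days | 66 days |
|---|---|---|
| 30 days | 42.6% | 78.2% |
| 40 days | 34.0% | 68.1% |
| 50 days | 28.3% | 59.9% |

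**Why recency matters.** The relative fall does not depend on when the last dose was given, but the amount left to lose does. With H = 40 and biopsies 28 days apart:

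| Last dose to baseline biopsy | Dose remaining, first to second biopsy | Fall in points |
|---|---|---|
| 22 days | 68.3% to 42.0% | 26.3 |
| 90 days | 21.0% to 12.9% | 8.1 |
| 180 days | 4.4% to 2.7% | 1.7 |

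The problem is confined to recent users, and time since last injection is the variable that identifies them.

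**Example.** On monthly 500 mg, the steady-state peak is 500 / (1 − 2^(−28/40)) = 1301 mg. With the last dose 22 to 30 days before Cycle 1 Day 1, 888 to 773 mg remain on that day. At Days 25 to 29, 586 to 476 mg remain.

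**Effect on the planned 17.4.4 correlation.** Suppose a fraction f are recent users, and recent use shifts ER change by d SD and shrinkage by e SD. The spurious correlation is f(1−f)de / √[(1 + f(1−f)d²)(1 + f(1−f)e²)].
- f = 0.5, d = 1, e = 0.5: 0.125 / √(1.25 × 1.0625) = 0.11.
- f = 0.5, d = e = 1: 0.25 / 1.25 = 0.20.

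Both lie below the roughly 0.31 needed for significance with 40 patients. If recency is unrelated to shrinkage (e = 0), the result is zero and wash-out only adds noise. f, d and e are assumptions.

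**Cost of adjustment.** With about 40 patients per arm (90% of 45, carrying over the tissue rate in 17.4.3) and a correlation of 0.35, power is Φ(0.365 × √37 − 1.96) = 60% unadjusted and Φ(0.365 × √36 − 1.96) = 59% with one covariate.

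**The case against.** The strongest reply is that the plan contains no test of whether ER rose. Section 17.4.4 relates ER change to shrinkage, and nowhere do the documents say that an Arm 1 rise will be credited to alisertib. A reader might infer a high false-positive rate for ER restoration. The documents do not support one: no such test is planned, and neither the share of recent users nor the ER response to falling drug is given. Prior fulvestrant may have been long ago, since endocrine lines are unlimited and up to two chemotherapy regimens are allowed. This part of the reply stands. What remains is that Objective 2.3.2 asks about ER change and the plan gives no way to read it.

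Second, a fall in drug is not a rise in ER. Section 8.2.1 says the effect is dose-related but gives no slope, and in the example above about one full dose remains at the second biopsy. That also stands: the direction of the bias follows from the documents, its size does not.

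Third, section 1 says that patients with ER-negative metastases are enrolled to test the restoration hypothesis, and 4.1.5 exempts those with such a history from prior fulvestrant. Wash-out is probably weakest there. But Objective 2.3.2 covers all patients, and section 3.4 frames the hypothesis for disease resistant to fulvestrant.

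Finally, 6.2.2 might be read as contradicting 17.4.4. It does not. It is an Arm 2 dosing rule, and shows only that the plan treats recent fulvestrant as relevant in one place and leaves it out in another.

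**Conclusion.** The concern holds as an identification problem in a correlative objective. In Arm 1 patients recently on fulvestrant, residual drug falls by 34% to 68% between biopsies 24 to 66 days apart at a 40-day half-life (28% to 78% across half-lives of 50 to 30 days). An ER rise in these patients cannot be attributed to alisertib unless time since last fulvestrant is shown.

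This rests on first-order loss, on the 250 mg half-life applying at 500 mg, and on ER recovering to some degree as fulvestrant clears. No false-positive rate and no size of ER shift can be stated. The bias in the 17.4.4 correlation is probably small, although the illustrative 0.11 and 0.20 are not bounds. The sample size, alpha and power for response are unaffected, and no direction is claimed for Arm 2. The change is worth making because it is cheap and decides what the trial can say about its central mechanism.

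**What to change.** Add to 17.4.4:

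> For Objective 2.3.2, change from baseline to end of Cycle 1 in tumor ER alpha (absolute change where baseline staining is 0%) and in ER target genes will be summarised by arm and by time from last fulvestrant injection to baseline biopsy: 80 days or less; more than 80 days; never. ER change will be plotted against days since last fulvestrant. As a sensitivity analysis, the correlation of ER change with tumor shrinkage will be repeated as a partial Spearman correlation adjusting for days since last fulvestrant, among patients previously exposed. The report will state that wash-out and alisertib effect cannot be separated in Arm 1 patients with recent fulvestrant.

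Eighty days is two stated half-lives: 25% of the dose remains (16% to 33% for half-lives of 30 to 50 days). The cut is a convention, so the plot is needed beside it. The never-exposed must stand apart, because under 4.1.5 they are patients with a history of ER-negative metastatic disease and differ in baseline ER by design. For the same reason, and because the subgroups will be small, no pass/fail rule should make an alisertib effect depend on what one group shows; a real effect could be dismissed for lack of data.

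Cost: one paragraph, one descriptive split, one plot, and about one point of power in the sensitivity analysis. No new patients, biopsies or visits are needed. Sites must know the last-injection date to apply 4.3.1 and 6.2.2, but it must be confirmed that the prior-therapy form listed in 14.1.2 captures it. The downside is small subgroups and a descriptive result only.

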**Note: Cycle 1 Day15: The morning dose of alisertib should be taken prior to Cycle 1 Day15 blood draws.**

### 6.3 Concomitant Treatment and Supportive Care Guidelines

- 6.3.1 Pre-treatment anti-emetics are not recommended prior to Cycle 1. Supportive care pre-treatment medications may be added with subsequent cycles per discretion of the treating oncologist.
- 6.3.2 Blood products and growth factors should be utilized as clinically warranted and following institutional policies and recommendations. The use of growth factors should follow published guidelines of the American Society of Clinical Oncology (42) 2006 Update of Recommendation for the Use of White Blood Cell Growth Factors: An Evidence-Based Clinical Practice Guideline Journal of Clinical Oncology 2006; 24(19):3187-3205.
- 6.3.3 Patients should receive full supportive care while on this study. This includes blood product support, antibiotic treatment, and treatment of other newly diagnosed or concurrent medical conditions. All blood products and concomitant medications such as antidiarrheals, analgesics, and/or antiemetics received from the first day of study treatment administration until 30 days after the final dose will be recorded in the medical records.
- 6.3.4 Diarrhea: This event could be managed conservatively with loperamide. The recommended dose of loperamide is 4 mg at first onset, followed by 2 mg every 2-4 hours until diarrhea free (maximum 16 mg/day). In the event of Grade 3 or 4 diarrhea, the following supportive measures are allowed: hydration, octreotide, and antidiarrheals. If diarrhea is severe (requiring intravenous rehydration) and/or associated with fever or severe neutropenia (Grade 3 or 4), broad-spectrum antibiotics must be prescribed. Patients with severe diarrhea or any diarrhea associated with severe nausea or vomiting **should be hospitalized** for intravenous hydration and correction of electrolyte imbalances.
- 6.3.5 Zoledronic acid, pamidronate, or denosumab may be administered per institutional guidelines as appropriate for patients with bone metastases.
- 6.3.6 PPI and histamine-2 (H2) receptor antagonists are not permitted.
- 6.3.7 Neutralizing antacids and calcium-containing supplements cannot be taken from 2 hours prior to alisertib dosing until up to 2 hours after dosing.
- 6.3.8 Concomitant use of moderate or strong CYP3A4 inhibitors (including but not limited to: clarithromycin, itraconazole, voriconazole, ketoconazole,

posaconazole, nefazodone, telithromycin, aprepitant, erythromycin, fluconazole, verapamil, diltiazem) or grapefruit juice/grapefruit-containing products should be avoided. Selection of an alternate concomitant medication with no or minimal CYP3A4 inhibition potential is recommended. If co-administration of moderate or strong CYP3A4 inhibitors is medically necessary, investigators should monitor for toxicities and follow the dose modifications per study protocol.

#### 6.4 Treatment/Follow-up Decision at Evaluation of Patient

- 6.4.1 Patients who have not had systemic disease progression and have experienced acceptable toxicity will be eligible for re-treatment at their current dose level until disease progression, unacceptable toxicity, or refusal.
- 6.4.2 Those patients who have not progressed and who have experienced unacceptable toxicity may be eligible for re-treatment at a lower dose. See Section 7.
- 6.4.3 Patients randomized to the alisertib alone arm that progress may begin treatment with fulvestrant and alisertib if the conditions listed in Section 6.1 are met.

Patients who are not eligible to continue on to fulvestrant plus alisertib or who choose not to continue on to fulvestrant plus alisertib will proceed to the Event Monitoring phase where patients will be followed every 6 months until death or a maximum of 5 years post-randomization for disease progression and death information.

Patients who proceed with fulvestrant plus alisertib treatment will continue until: disease progression, patient request, intolerability, or refusal.

- 6.4.4 Criteria for discontinuation of all protocol therapy include:
- Tumor progression during combination treatment with fulvestrant and alisertib
  - Arm 1 only: tumor progression during alisertib and patient will not be switching to combination treatment with fulvestrant and alisertib
  - Request by the patient to withdraw from all protocol treatment
  - Unacceptable adverse events
  - Treatment delay of >21 days (exception: recovery from Cycle 1 Day 15 severe neutropenia where treatment delay of >30 days triggers treatment discontinuation [see Section 7.3])
  - Intercurrent illness which would, in the judgment of the investigator, affect assessments of clinical status to a significant degree that require discontinuation of drug
  - Administration of radiotherapy, non-protocol chemotherapy, or an experimental drug during the trial

Patients who discontinue treatment for any of the above reasons will go to event monitoring. Once a patient has entered the event monitoring phase of the trial, his/her therapy is at the discretion of the treating physician.

- 6.4.5 If an eligible patient refuses treatment following registration (and is classified as a “cancel” by the Research Base), all on-study materials must be submitted to the Research Base.
- 6.4.6 A patient is deemed *ineligible* if at the time of registration, the patient did not satisfy each and every eligibility criteria for study entry.
- If the patient never received any study treatment, on-study materials (with the exception of biospecimens) must be submitted. No further follow-up is required.
  - If the patient is receiving study treatment at the time the ineligibility is discovered, the patient may continue on study at the discretion of the treating physician as long as there are no safety concerns, and the patient was properly registered. All protocol procedures must be followed. Otherwise, the patient enters the event monitoring phase of the study.
- 6.4.7 If protocol requirements regarding treatment in Cycle 1 of the initial therapy are severely violated to the point the Study Team finds that the patient is not evaluable for primary end point, the patient will be flagged in to study database as a protocol violation. The patient may continue on study at the discretion of the treating physician as long as there are no safety concerns, and the patient was properly registered. All protocol procedures must be followed. Otherwise, no further follow-up is required.
- 6.4.8 If a patient withdraws consent prior to receiving any study treatment or is found to have unacceptable liver enzyme levels [either (1) total bilirubin >1.5 x ULN or (2) alanine transaminase >5 x ULN] on Cycle 1 Day 1 and does not receive protocol treatment, the patient will be deemed a *cancel*. On-study material (with the exception of biospecimens) and the End of Active Treatment/Cancel Notification Form must be submitted. For patients who are cancelled due to unacceptable liver enzyme levels on Cycle 1 Day 1. A comment should be added to the CRF stating that the patient had unacceptable liver enzyme levels on Cycle 1 Day 1 and did not start treatment. No further data submission is necessary.

